5.5. Supportive Care Guidelines

- Medications may be administered for the management of symptoms associated with the administration of FF-10501-01, as required.
- Prophylactic pre-medication will not be used routinely. Adequate treatment for nausea and/or vomiting and diarrhea is permitted during Cycle 1. After Cycle 1, prophylaxis of nausea and/or vomiting and diarrhea is permitted.
- Granulocyte stimulating growth factors (e.g., G-CSF or GM-CSF) are not allowed during Cycle 1 except for the following situations (defined as DLTs): Grade 4 neutropenia lasting 7 days or more, or failure of the absolute neutrophil count (ANC) to recover to Grade 1 within 12 weeks. After Cycle 1, use of granulocyte growth factors are allowed for prophylaxis or management of neutropenia.
- Erythropoiesis-stimulating agents, transfusions, etc. are permitted for management of hematologic toxicities.

5.6. Prior and Concomitant Medications and Therapies

5.6.1. Permitted Medications

All medications and other treatments taken by subjects 4 weeks before and throughout the study period will be recorded in the CRF module. Any changes in documented, permitted concomitant medications being taken at the beginning of the clinical trial or added during the time the subject is participating in this study must be recorded in the CRF module.

5.6.2. Prohibited Therapy

Concurrent anti-tumor therapy of any kind or any other investigational agent is prohibited. Concomitant medication(s) that may cause QTc prolongation or induce Torsades de Pointes are prohibited, with the exception of anti-microbials that are used as standard of care to prevent or treat infections and other such drugs that are considered by the Investigator to be essential for the care of the patient. See **Appendix C** for a list of drugs that may cause QTc prolongation or induce Torsades de Pointes.

5.7. Packaging and Labeling

FF-10501-01 will be supplied in 50 and 200 mg tablets for oral dosing. The study drug will be packaged in bottles labeled with pill strength and other information as per local regulatory requirements.

5.8. Shipping and Storage

The drug product has been demonstrated to be stable when stored in the defined container closure, high density polyethylene (HDPE) bottles. FF-10501-01 should be stored at room temperature (20 – 25 °C).

5.9. Drug Accountability

The investigator must maintain accurate records of receipt of study drug, dispensing information, and the prompt return or destruction of unused supplies. A drug accountability log will be supplied to each clinical site for purposes of recording study drug dispensation for the study and will be monitored by sponsor personnel. If the site has an electronic study drug accountability form that is in keeping with institutional practice and the form collects the same information as the form supplied by the Sponsor, this form may be substituted for the Sponsor's drug accountability form.

Unused or expired FF-10501-01 tablets will be destroyed per institutional policy.

6. STUDY PROCEDURES

See Schedule of Study Procedures in **Appendix D**.

6.1. Screening Procedures

The following evaluation includes standard tests are to be performed within 28 days of study treatment to determine subject eligibility.

- Administration of informed consent
- Medical history, physical examination and vital signs
- ECOG Performance Status
- Height and weight
- The following lab tests:
 - Hematology
 - Serum chemistry
 - Urinalysis
- Beta HCG for WCBP
- 12-lead ECG
- Review of concomitant medications
- Disease-specific assessment (BM aspirate)

6.2. Requirements During Treatment Cycle 1

6.2.1. *Cycle 1, Day 1*

- Abbreviated physical examination
- Vital signs
- ECOG Performance Status
- Weight
- The following lab tests:
 - Hematology, if not performed within the previous 24 hours
 - Serum chemistry, if not performed within the previous 24 hours
 - Urinalysis, if not performed within the previous 24 hours
- 12-lead ECG, pre-dose and approximately 3 hours post-dose (following morning dose only)
- Review of concomitant medications
- Assessment of adverse events
- For subjects on 21-day dosing schedules: Peripheral blood collection in heparin for PK and XMP assessments, pre-dose (any time), between 0.5-1 hr post-dose, and between 2-4 hr post-dose
- For subjects on 21-day dosing schedule: Dispense 21-day supply of FF-10501-01 study drug for Cycle 1
- Assessment for survival

6.2.2. *Cycle 1, Day 8 (+/- 1 day)*

- Vital signs
- The following lab tests:
 - Hematology
 - Serum chemistry
- Review of concomitant medications
- Assessment of adverse events
- Review subject medication diary for FF-10501-01 study drug
- Assessment for survival

6.2.3. *Cycle 1, Day 15 (+/- 1 day)*

- Vital signs
- The following lab tests:

- Hematology
- Serum chemistry
- 12-lead ECG, pre-dose and approximately 3 hours post-dose (following morning dose only)
- Review of concomitant medications
- Assessment of adverse events
- For subjects on 21-day dosing schedules: Peripheral blood collection in heparin for PK and XMP assessments, pre-dose (within 15 minutes prior to dosing), between 0.5-1 hr post-dose, and between 2-4 hr post-dose
- Assessment for survival

6.2.4. Cycle 1, Day 22 (+/- 1 day)

- Vital signs
- The following lab tests:
 - Hematology
 - Serum chemistry
- Review of concomitant medications
- Assessment of adverse events
- Assessment for survival

6.2.5. End of Cycle 1 (Day 28 +/- 3 days)

- Bone marrow aspirate (unless peripheral blood absolute blast count is $\geq 5.0 \times 10^9$ cells/L)
- Disease Response Assessment
- Review of concomitant medications
- Assessment of adverse events
- Assessment for survival

6.3. Requirements During Treatment Cycles After Cycle 1 (Cycles 2, 3, 4, etc.)

6.3.1. Day 1 (+/- 3 days, except for pre-dose procedures; ECG)

- Abbreviated physical examination
- Vital signs
- ECOG Performance Status
- Weight

- The following lab tests (within 3 days of each cycle):
 - Hematology
 - Serum chemistry
 - Urinalysis
- 12-lead ECG, pre-dose and approximately 3 hours post-dose (following morning dose only)
- Review of concomitant medications
- Assessment of adverse events
- Assessment for survival
- For subjects on 21-day dosing schedule: Dispense 21-day supply of FF-10501-01 study drug for cycle

6.3.2. End of Cycle 3 and Every 2 Cycles Thereafter

- Bone marrow aspirate (unless peripheral blood absolute blast count is $\geq 5.0 \times 10^9$ cells/L)
- Review of concomitant medications
- Assessment of adverse events
- Disease Response Assessment
- Assessment for survival

6.4. At Relapse or Progression of Disease

- Bone marrow aspirate (unless peripheral blood absolute blast count is $\geq 5.0 \times 10^9$ cells/L)
- Review of concomitant medications
- Assessment of adverse events
- Disease Response Assessment
- Assessment for survival

6.5. End of Study (Safety Visit, 28 days \pm 5 days after the last dose of study drug)

- Physical examination
- Vital signs
- ECOG Performance Status
- Weight
- The following lab tests:
 - Hematology

- Serum chemistry
- Urinalysis
- 12-lead ECG
- Review of concomitant medications
- Assessment of adverse events
- Assessment for survival

6.6. Long-term Follow-up

Long-term follow-up will consist of a clinic visit or telephone call to assess survival every 3 months for up to 6 months.

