1.7.2. U.S. Phase 1/2a Study

Study FF1050101US101 is ongoing in the United States in patients with AML, MDS or CMML. In Phase 1, dose levels of 50, 100, 200, 300, 400 and 500 mg/m² BID for 14 days, followed by 14 days off therapy, or 400 mg/m² BID for 21 days, followed by 7 days off therapy, repeated every 28 days have been studied to date. A total of 33 patients have been treated to date on study (25 AML, 8 MDS).

Three events of drug-related atrial fibrillation (Grade 2) were reported in 2 subjects at a dose of 500 mg/m² BID (Cohort 6). Study drug was suspended in both subjects and all events resolved with oral metoprolol treatment. These events were medically important events and thus met the definition of dose-limiting toxicity (DLT). No further enrollment was made at this dose level. The maximally tolerated dose (MTD) was declared at 1 dose level below the dose eliciting DLT, 400 mg/m² BID, and this cohort was expanded to 6 subjects. No DLTs have been observed in N=7 total subjects treated at 400 mg/m² BID x 14 days.

At the MTD of 400 mg/m² BID, Cohort 7 was added to extend the BID dosing schedule to 21 days followed by 7 days off, repeated every 28 days (=1 cycle) (Amendment 3). No DLTs occurred have occurred to date.

At the MTD of 400 mg/m² BID, Cohort 8 was added to extend the BID dosing schedule to 28 days continuous dosing (=1 cycle) (Amendment 4). No DLTs have occurred to date.

The median number of prior treatments is 2 (range 1 - 7), all relapsed or refractory to prior hypomethylating agents (azacitidine, decitabine). The median number of treatment cycles is 2 (range 1 – 28).

The most common AEs include Grade 1 or 2 fatigue, diarrhea, and nausea, with drug-related Grade 3 or 4 AEs reported for 1 patient in the 200 mg/m² BID dose group (thrombocytopenia, neutropenia and bone marrow aplasia) and 1 patient in the 300 mg/m² BID dose group (mucositis); the events resolved without sequelae.

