3.3. Duration of Study

The accrual phase for the Phase 1 dose-escalation phase is expected to be 12 – 18 months. The expected accrual phase for the Phase 2a expansion phase is expected to be 6 – 12 months, with the last subject followed for up to 6 months, for a total study duration of 30 – 36 months. The anticipated accrual rate for the Phase 2a portion is 4 – 5 subjects per month.

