5.3. Treatment Duration

Treatment will continue until confirmation of disease progression, unacceptable toxicity, or subject decision to discontinue therapy

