8.3.2.2. Secondary Efficacy Endpoints

The proportion of MDS subjects with hematologic improvement in the peripheral blood or bone marrow as defined as $\geq 50\%$ reduction in blast count when compared with the baseline value. The 90% confidence interval will be estimated and provided.

Progression-free survival and overall survival curves will be estimated at the MTD by disease cohort using Kaplan-Meier product limit estimates. Median and 90% confidence interval of time-to-event will be estimated. Progression-free survival will be calculated from the date of first dose of study drug to the date of first objective evidence of disease progression or death, whichever is earlier. Overall survival will be calculated from the date of first dose of study drug to the date of death due to any cause. Subjects who did not experience progression or death will be censored at the last follow-up time point.

8.3.3. *Pharmacokinetic Endpoint Analysis*

Mean plasma concentrations of FF-10501 and plasma M1 will be determined at each time point for evaluation of dose-linearity. Because a limited number of plasma concentrations will be determined, full determination of routine pharmacokinetic parameters may not be possible. In addition to mean plasma concentrations, as the data allow, additional pharmacokinetic analyses will be provided (trough levels, $t_{1/2}$, T_{max} , C_{max} , AUC, etc.)

8.3.4. *Pharmacodynamic Endpoint Analysis*

Change from baseline in XMP levels will be measured in blood samples collected from each subject during the study. Correlations between XMP and PK levels of FF-10501 will be made. Pharmacodynamic parameters will be summarized using descriptive statistics

including the number of subjects, mean, standard deviation, minimum, median, maximum, range, and coefficient of variation.

8.3.5. *Other Summaries*

Demographics and concomitant medications, including antibiotic usage, will be summarized using descriptive statistics. Medical history findings and protocol deviations will be listed but not summarized.

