^h Subjects on the 21-day dosing schedules: Peripheral blood collected in heparin for PK and PD assessment at Cycle 1, Day 1 pre-dose (any time), between 0.5-1 hr post-dose, and between 2-4 hr post-dose, and Cycle 1 Day 15 pre-dose (within 15 min prior to dosing), 0.5-1 hr post-dose, and 2-4 hr post-dose.

ⁱ Subjects on 21-day schedule, dose BID daily x 21 days each 28-day cycle

^j Abbreviated physical exam

^k Day 8, 15, or 22 +/- 1 day, except for pre-dose procedures for the cycle (e.g., ECG)

^l Day 28 +/- 3 days

^m Day 1 +/- 3 days except, for pre-dose procedures for the cycle (e.g., ECG)

ⁿ And every 2 cycles thereafter

^o End of Study (Safety) visit should be 28 days from last dose of study medication (+/- 5 days)

^p Long-term follow-up for 6 months consists of clinic visits or telephone calls every 3 months to assess survival status

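### Survival follow-up appears to end about 6–7 months after last dose, so each subject's OS observation depends on time on drug; the late OS curve will rest on few subjects and may be biased upward

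*Protocol*

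**What the plan says.** OS is a secondary objective (Protocol 2.2, SAP 1.2.2). Protocol 8.3.2.2 defines it: "Overall survival will be calculated from the date of first dose of study drug to the date of death due to any cause". The method in the same section is: "Progression-free survival and overall survival curves will be estimated at the MTD by disease cohort using Kaplan-Meier product limit estimates", with a median and 90% confidence interval. Subjects without an event are censored at their last follow-up.

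How long a subject is observed follows from four other places:

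- Protocol 5.3: "Treatment will continue until confirmation of disease progression, unacceptable toxicity, or subject decision to discontinue therapy".
- Protocol 6.5 and Appendix D: the End of Study visit falls 28 days (± 5) after last dose.
- Protocol 6.6: "Long-term follow-up will consist of a clinic visit or telephone call to assess survival every 3 months for up to 6 months". Appendix D, footnote p, agrees: "Long-term follow-up for 6 months consists of clinic visits or telephone calls every 3 months to assess survival status". In the schedule this column comes after the End of Study visit.
- Protocol 3.3: the study runs 30–36 months in all, "with the last subject followed for up to 6 months".

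Survival status is also checked at every visit on treatment. SAP 3.3.2 repeats the OS definition, and SAP 4.1.5 and 4.2 list an OS table and graph. The SAP adds no common cut-off date, no OS censoring rule and no limit on how far the curve is drawn. On time on drug so far, Protocol 1.7.2 reports: "The median number of treatment cycles is 2" (range 1–28).

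**The concern.** OS is counted from first dose, but the clock that ends observation is tied to last dose. Maximum OS observation is therefore time on drug plus about 6–7 months. Progression is one of the reasons for stopping drug, so the event that worsens the outlook also starts the countdown to censoring.

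Two consequences follow. First, subjects who stop early leave the risk set at about 7–9 months even if alive, so later estimates rest on few people. This needs no assumption about bias. Second, Kaplan-Meier treats the censored subjects as having the same future risk as those still observed. If subjects off drug die faster than subjects on drug, the late curve is too high. With no comparator arm, nothing else in the trial would reveal this. Early subjects also go out of contact while the sites are still open.

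**Working it through.** The documents give no OS event count or precision target, so there is no planned OS figure to reproduce.

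**Step 1: last possible contact.** Inputs from the Protocol: 28-day cycles with 21 dosing days, End of Study visit at last dose + 28 days, then 6 months (183 days). For a subject who stops after *c* cycles without delays:

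last contact day = 28(*c* − 1) + 21 + 28 + 183

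- *c* = 1: 0 + 21 + 211 = Day 232, or 7.6 months
- *c* = 2: 28 + 21 + 211 = Day 260, or 8.5 months
- *c* = 14: 364 + 21 + 211 = Day 596, or 19.6 months
- *c* = 28: 756 + 21 + 211 = Day 988, or 32.5 months

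If the 6 months start at last dose instead, each figure falls by 28 days: Day 204 (6.7 months) for 1 cycle and Day 232 (7.6 months) for 2.

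**Step 2: who can be observed at 12 months.** Last dose must be on or after Day 365 − 211 = 154, which lies in cycle 6. That is three times the Phase 1 median. Protocol 1.7.2 indicates who such subjects are: the 4 of 8 MDS patients with disease control had it over 3, 5, 14 and 17 cycles.

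**Step 3: size of the effect.** Simulation, 400,000 subjects per scenario, comparing Kaplan-Meier under this follow-up with true survival. From the documents: median 2 cycles, 6 months of follow-up, groups of 20 for scale. Assumed, not in the documents: median survival after stopping of 3, 5 or 8 months; off-drug death hazard 1 or 3 times the on-drug hazard; either no shared frailty or frailty (log-SD 0.7) linking time on drug with survival; censoring at 6.0 or 6.9 months after last dose. Four of the scenarios:

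| Scenario | S(12) true / KM | S(18) true / KM | At risk per 20 at 12 months (if followed fully) | Median OS, months, true / KM |
|---|---|---|---|---|
| 2 cycles, post-drug median 8 months, hazard ratio 1, no frailty, 6.9 months | 0.352 / 0.352 | 0.208 / 0.207 | 1.0 (7.0) | 8.0 / 8.0 |
| 2 cycles, post-drug median 5 months, ratio 3, no frailty, 6.9 months | 0.249 / 0.255 | 0.109 / 0.119 | 1.1 (5.0) | 6.8 / 6.8 |
| 2 cycles, post-drug median 8 months, ratio 3, frailty, 6.0 months | 0.422 / 0.473 | 0.291 / 0.391 | 2.5 (8.4) | 9.5 / 10.7 |
| 4 cycles, post-drug median 8 months, ratio 3, frailty, 6.9 months | 0.471 / 0.496 | 0.331 / 0.395 | 5.5 (9.4) | 11.0 / 11.8 |

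Across the median-2-cycle scenarios:

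- Bias at 6 months is 0 in every one.
- With no link between stopping and death, bias is about 0 throughout.
- With a link, bias is +0.4 to +5.1 points at 12 months and +0.5 to +10.0 at 18 months.
- At risk at 12 months: 0.1–3.0 per 20, against 1.2–8.4 with full follow-up.

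**Step 4: second model as a check.** Lognormal cycles (log-SD 0.8–1.0), no frailty, deaths allowed on drug, 6.9 months of follow-up. With median 2 cycles and an off-drug hazard 2–3 times the on-drug hazard, bias is about +0.3 to +1.3 points at 12 months and about +1 to +3.4 at 18 months. With median 4 cycles, both models together put about 2–6 per 20 at risk at 12 months.

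**The case against.** Several objections have force.

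- **The start of the 6 months is not written down.** Correct. It is inferred from the order of 6.5 and 6.6 and the Appendix D columns. That limits how firmly the point can be put, and is itself a reason to amend 6.6.
- **The bias is conditional.** A reader might infer that the late OS curve must be too high. The documents do not support that: they give no figure linking stopping drug with survival, and without a link the bias is about 0. A link is likely, since progression ends treatment, but its size is assumed. Models in which nobody dies on drug give larger values and should not be taken as typical.
- **The median of 2 cycles may not carry over.** It comes from 33 Phase 1 patients, 25 with AML, over several doses and schedules, in an ongoing study. A reader might infer that only one or two of the 20 Phase 2a subjects will be at risk at 12 months. Phase 2a excludes AML, so that does not follow; hence the 4-cycle sensitivity.
- **The planned summary is a median, not 12- or 18-month OS.** Largely accepted. The median hardly moves when it is below about 8 months. The curve is still planned, and will be read at later times.
- **Sampling error dominates.** With 20 subjects and S = 0.36, the 90% half-width is 1.645 × √(0.36 × 0.64 / 20) = 0.18, even with complete follow-up. That makes the bias modest in comparison; it does not justify discarding late observation time.
- **OS drives no decision.** True: safety is primary and SAP 2.4.2 plans no tests.

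What stands is the dependence of follow-up on time on drug, and the loss of subjects at risk after about 7–9 months.

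**Conclusion.** The point holds as a modest, cheaply corrected weakness. The firm part rests on the Protocol's own intervals, given the implied start of follow-up: OS observation ends at about 7.6 months after 1 cycle and 8.5 after 2, with no common cut-off. Numbers at risk at 12 months then fall to roughly 0–3 per 20 with median 2 cycles, or about 2–6 with median 4.

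The conditional part is the upward bias. It is 0 at 6 months, about 0 to +5 points at 12 months and 0 to +10 at 18 months under the assumed models, towards the lower end if the off-drug hazard is only 2–3 times the on-drug hazard, and about 0 with no link. Median OS can be overstated by about 1–2 months when the true value is longer than about 8 months. It would go too far to call the OS analysis invalid or its median unreliable in general. No test, sample size or decision rule is affected.

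**What to change.** **Protocol 6.6 and Appendix D footnote p.** State when long-term follow-up starts. Replace the 6-month limit with survival status by telephone every 3 months until death, withdrawal of consent or one common study cut-off, defined as the end of the last subject's 6-month follow-up. For subjects already past 6 months, make one status check at the cut-off where consent allows. OS observation then no longer depends on time on drug, and this bias disappears in every scenario modelled.

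**Protocol 8.3.2.2 and SAP 3.3.2.** Report 6-month OS from first dose, which planned follow-up covers for every subject. Show numbers at risk under the curve. If follow-up is not extended, flag or truncate the curve beyond 6 months.

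**Cost.** The follow-up change needs a protocol amendment with IRB approval (Protocol 9.4), possibly consent wording, and a few telephone contacts while the study is open. The reporting changes need wording only and are worth making even if the extension is declined.

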7. DESCRIPTION OF ASSESSMENTS

7.1. Safety Assessments

7.1.1. *Adverse Event Definition*

An adverse event (AE) includes any noxious, pathological, or unintended change in anatomical, physiological, or metabolic functions as indicated by physical signs, symptoms, and/or laboratory changes occurring whether or not temporally associated with study drug administration and whether or not considered related to study drug. This definition includes an exacerbation of pre-existing medical conditions or events, intercurrent illnesses, hypersensitivity reactions, drug interactions, or clinically significant laboratory findings.

An AE does **not** include the following:

- Medical or surgical procedures, e.g., tooth extraction, transfusion, surgery (The medical condition that leads to the procedure is to be recorded as an AE.)
- Pre-existing conditions or procedures present or detected at the start of the study that do not worsen
- Hospitalization for elective surgeries or for other situations in which an untoward medical event has not occurred
- Abnormal laboratory value, unless it is clinically significant
- Overdose of study drug or concomitant medication unaccompanied by signs/symptoms (If sign/symptoms occur, the final diagnosis should be recorded as an AE.)
- Pregnancy by itself, unless a complication occurs during pregnancy leading to hospitalization; in this case (The medical condition that leads to the hospitalization is to be recorded as the AE.)
- A significant worsening of the disease under investigation which is captured as an efficacy parameter in this study and, thus, is not to be recorded as an AE.

7.1.2. Serious Adverse Event

A serious adverse event (SAE) is defined as an adverse event that results in any of the following outcomes:

- Death
- Life-threatening, i.e., immediate risk of death from the event as it occurred; (This does not include an adverse event that, had it occurred in a more serious form, might have caused death.)
- Persistent or substantial disability/incapacitation
- Results in or prolongs an existing inpatient hospitalization
- Congenital anomaly/birth defect

Important medical events that may not result in death, be life-threatening, or require hospitalization may be considered serious when, based on medical judgment, they may jeopardize the subject or may require medical or surgical intervention to prevent one of the outcomes listed in this definition.

